16.0 MULTICENTER REGULATORY REQUIREMENTS

Washington University requires that each participating site sends its informed consent document to be reviewed and approved by the Washington University Regulatory Coordinator (or designee) prior to IRB/IEC submission.

Site activation is defined as when the secondary site has received official written documentation from the coordinating center that the site has been approved to begin enrollment. At a minimum, each participating institution must have the following documents on file at Washington University prior to study activation:

- Documentation of IRB approval of the study in the form of a letter or other official document from the participating institution's IRB. This documentation must show which version of the protocol was approved by the IRB.
- Documentation of IRB approval of an informed consent form. The consent must include a statement that data will be shared with Washington University, including the Quality Assurance and Safety Monitoring Committee (QASMC), the DSMC (if applicable), and the Washington University study team.
- Documentation of FWA, signed FDA Form 1572 (if applicable), and the CVs of all participating investigators.
- Protocol signature page signed and dated by the investigator at each participating site.

The coordinating center Principal Investigator (or designee) is responsible for disseminating to the participating sites all study updates, amendments, reportable adverse events, etc. Protocol/consent modifications and IB updates will be forwarded electronically to the secondary sites within 4 weeks of obtaining Washington University IRB approval. Activated secondary sites are expected

to submit protocol/consent/IB modifications to their local IRBs within 4 weeks of receipt unless otherwise noted. Upon the secondary sites obtaining local IRB approval, documentation of such shall be sent to the Washington University study team within 2 weeks of receipt of approval.

Documentation of participating sites' IRB approval of annual continuing reviews, protocol amendments or revisions, all SAE reports, and all protocol violations/deviations/exceptions must be kept on file at Washington University.

The investigator or a designee from each institution must participate in a regular conference call to update and inform regarding the progress of the trial.

APPENDIX A: ECOG Performance Status Scale

Grade	Description
0	Normal activity. Fully active, able to carry on all pre-disease performance without restriction.
1	Symptoms, but ambulatory. Restricted in physically strenuous activity, but ambulatory and able to carry out work of a light or sedentary nature (e.g., light housework, office work).
2	In bed <50% of the time. Ambulatory and capable of all self-care, but unable to carry out any work activities. Up and about more than 50% of waking hours.
3	In bed >50% of the time. Capable of only limited self-care, confined to bed or chair more than 50% of waking hours.
4	100% bedridden. Completely disabled. Cannot carry on any self-care. Totally confined to bed or chair.
5	Dead.

APPENDIX B: PALBOCICLIB MEDICATION DIARY

Today's Date: _____

Agent: Palbociclib

Cycle: _____

Study ID#: _____

INSTRUCTIONS TO THE PATIENT:

1. Complete one form for each month. Take _____mg (____capsules) of palbociclib with food on a 5 days on/2 days off schedule. Take the palbociclib with a glass of water and drink the glass of water in as little time as possible. Swallow the capsules whole and do not chew the capsules.
2. Record the date, the number of capsules taken, and when you took them.
3. If you forget to take your palbociclib dose before 6:00PM, then do not take a dose that day. Restart taking it the next day.
4. If you have any questions or notice any side effects, please record them in the comments section. Record the time if you should vomit.
5. Please return the forms to your physician or your study coordinator when you go to your next appointment. Please bring your unused study medications and/or empty bottles with you to each clinic visit so that a pill count can be done.

Day	Date	What time was dose taken?	# of capsules taken	Comments
1				
2				
3				
4				
5				
6				
7				
8				
9				
10				
11				
12				
13				
14				
15				
16				
17				
18				
19				
20				
21				
22				
23				
24				
25				
26				
27				
28				

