5.0 TREATMENT PLAN

5.1 Agent Administration

Agent	Dose	Route	Schedule	Cycle Length
Palbociclib	125 mg	PO	5 days on and 2 days off, starting C1D1	28 days (4 weeks)
Letrozole*	2.5 mg	PO	Daily	
Fulvestrant*	500 mg	IM	Every 14 days for the first 3 doses followed by every 28 days	
Goserelin**	3.6 mg	SC	Every 28 days (Day 1 of each cycle)	
* Letrozole OR fulvestrant will be administered with palbociclib per physician choice. ** Only if pre- or peri-menopausal				

Patients will be instructed to make use of medication diaries (Appendices B and C) to act as records of administration for palbociclib and letrozole (if applicable).

Palbociclib at a dose of 125 mg should be taken by mouth with food on a 5 days on/2 days off schedule (meaning: on Days 1-5, 8-12, 15-19, and 22-26 of each 28-day cycle). If a patient misses a day's dose entirely, she must be instructed not to make it up the next day but just take her regular dose at the next assigned time. If a patient vomits any time after taking a dose, she must be instructed not to retake the dose but resume subsequent dosing at the next assigned time. If a patient inadvertently takes an extra dose during a day, she must be instructed to not take the next day's dose.

Patients who have been on stable doses of palbociclib for 6 consecutive cycles can be assessed for retreatment every 2 or 3 cycles to coincide with imaging. These patients must meet retreatment criteria (as described in Section 6.4) and will have labs drawn for retreatment (CBC with differential and CMP) and correlative studies (serum, plasma, cell-free DNA, and circulating tumor cells) to correspond with imaging studies that take place every 2-3 cycles. This allows patients on stable doses of palbociclib to return to clinic for retreatment at greater intervals.

Patients who are receiving letrozole will take it daily by mouth, every day of each 28-day cycle, at a dose of 2.5 mg. If a patient misses a day's dose entirely, she must be instructed not to make it up the next day but just take her regular dose on the next day. If a patient vomits any time after taking a dose, she must be instructed not to retake the dose but resume subsequent dosing on the next day. If a patient inadvertently takes an extra dose during a day, she must be instructed to not take the next day's dose.

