8.1.5 Dosage Form and Preparation

Medication will be provided in non-patient specific bottles containing either 125 mg, 100 mg, or 75 mg capsules. The patient number and the protocol number should be recorded on the bottle label in the spaces provided. Site personnel must ensure that patients clearly understand the directions for self-medication. Patients should be given a sufficient supply to last until their next study visit. Unused drug and/or empty bottles should be returned to the site at the next study visit. Palbociclib is an agent that must be handled and administered with care. Patients should be instructed to keep their medication in the bottles provided and not transfer it to any other container. Due to possible unknown hazards associated with topical and environmental exposure to experimental agents, capsules must not be opened and/or emptied into any vehicle for oral ingestion; capsules must be swallowed intact.

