10.0 STUDY CALENDAR

Screening/baseline evaluations are to be conducted within 2 weeks prior to start of protocol therapy. Scans and x-rays must be done no more than 4 weeks prior to the start of the protocol therapy. There is a +/-3 day window around each study visit.

	Screening	Baseline	Day 1 of each cycle ⁸	C1D15	C2D1	C2D15	End of every 2 nd or 3 rd cycle ⁸	Time of progression	30 day f/u
Informed consent	X								
H&P, ECOG PS	X		X		X			X	
CBC w/diff	X		X	X	X	X			
CMP	X		X		X				
β-hCG ¹	X								
Imaging	X						X	X	
Palbociclib			Given on a 5 days on / 2 days off schedule for each 28-day cycle						
Fulvestrant ³			X	X	X				
Letrozole ³			Daily						
Goserelin ⁴			X		X				
Medication diary			Daily, to be returned at the end of each cycle						
AE assessment			X -----X						
Archival Tissue		X ⁷							
Research biopsy (optional)		X						X	
Blood for serum		X		X ⁵	X ⁵		X ^{2,5}	X	
Blood for plasma		X		X ⁵	X ⁵		X ^{2,5}	X	
Blood for cfDNA		X		X ⁵	X ⁵		X ^{2,5}	X	
Blood for germline DNA		X							
Blood for circulating tumor cells		X			X		X ⁶	X	

1. Women of childbearing potential only
2. Beginning with the end of Cycle 2 but to coincide with imaging studies
3. Either fulvestrant OR letrozole will be given (MD decision)
4. Goserelin will be given to premenopausal women only
5. Instruct patient take palbociclib/hormonal therapy after blood draw, meaning blood draw needs to happen prior to the day's treatment.
6. Post 2 or 3 months after start of therapy (to coincide with ONLY the 1st imaging assessment of tumor response)
7. Archival tissue should include both primary and metastatic tissue
8. Labs and office visits could be reduced in frequency to q2-3 cycles to coincide with tumor imaging studies in patients on stable doses of palbociclib for at least 6 consecutive cycle

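### The palbociclib diary's missed-dose instruction conflicts with Section 5.1 when the missed dose is the last of the week's five (Day 5, 12, 19 or 26)

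*Combined protocol and SAP*

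**What the plan says.** Section 5.1 assigns palbociclib "on Days 1-5, 8-12, 15-19, and 22-26 of each 28-day cycle", which is 20 dosing days and 8 off-days per cycle. For a missed palbociclib dose it says that "she must be instructed not to make it up the next day but just take her regular dose at the next assigned time". For letrozole, which is taken every day, the same section has the patient resume on the following day.

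Appendix B is the page the patient takes home. Item 1 tells her to take her dose "of palbociclib with food on a 5 days on/2 days off schedule". Item 3 reads: "If you forget to take your palbociclib dose before 6:00PM, then do not take a dose that day. Restart taking it the next day". It makes no exception for off-days. The form does not list the dosing days, and its grid has an open row for each of the 28 days. Item 3 of the letrozole diary (Appendix C) is the same apart from the drug name.

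Three other provisions bear on the point:

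- Section 5.1 on the status of the diary: "Patients will be instructed to make use of medication diaries (Appendices B and C) to act as records of administration".
- Section 8.1.5 on staff duties: "Site personnel must ensure that patients clearly understand the directions for self-medication".
- The Section 10.0 calendar entry for the diary: "Daily, to be returned at the end of each cycle".

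**The concern.** For a daily drug, the next day and the next assigned dose are always the same. On a 5/2 schedule they differ once a week, after the last on-day. On that day the diary, read literally, calls for the next-day dose that Section 5.1 rules out.

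The 5/2 schedule is the intervention under test. Section 1.3 argues for it partly on the ground that the marrow gets frequent rests from the drug. A dose on the first off-day breaks up that week's rest. The primary objective counts grade 3 or worse neutropenia over the first 29 days, so a departure in Cycle 1 falls inside the primary window. At stake is fidelity to the schedule, not the statistical design.

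**Working it through.** **Inputs.** Dosing days and the protocol's missed-dose rule come from Section 5.1, and the diary rule from Appendix B item 3. The CBC times and the visit window of 3 days either side come from Section 10.0. The sample size of 47 comes from Section 15.2. The plan states no figure for this point that could be reproduced.

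**Step 1: where the rules differ.** For each of the 20 dosing days, compare the next calendar day (diary) with the next assigned day (Section 5.1). They differ on four:

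| Missed day | Diary item 3, read literally | Section 5.1 |
|---|---|---|
| 5 | Day 6 (off-day) | Day 8 |
| 12 | Day 13 (off-day) | Day 15 |
| 19 | Day 20 (off-day) | Day 22 |
| 26 | Day 27 (off-day) | Day 29 (Day 1 of next cycle) |

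That is 4/20 = 20% of dosing days. On the other 16 the rules agree.

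**Step 2: what one such miss does to the cycle.**

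- Section 5.1: 20 − 1 = 19 doses. A Day 5 miss leaves three consecutive dose-free days (5, 6, 7).
- Diary: 20 − 1 + 1 = 20 doses. A Day 5 miss leaves two separated dose-free days (5 and 7), with a dose on Day 6 between them.

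The total never exceeds the planned 20. The diary asks for returned drug "so that a pill count can be done", but a count of 20 would look fully adherent. Only the dated diary row would show the off-day dose.

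**Step 3: dose-free days just before the nominal blood counts.**

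| | Planned | Section 5.1 | Diary |
|---|---|---|---|
| C1D15 CBC after a Day 12 miss | 2 (Days 13–14) | 3 (Days 12–14) | 1 (Day 14) |
| C2D1 (Day 29) CBC after a Day 26 miss | 2 (Days 27–28) | 3 (Days 26–28) | 1 (Day 28) |

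The visit window can shift these figures.

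**Step 4: how many patients could meet the situation.** The documents give no missed-dose rate. Assume independent misses with probability p per dose. The chance of missing at least one of the four days in Cycle 1 is 1 − (1 − p)^4:

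- p = 0.01: 1 − 0.99^4 = 0.0394, and 0.0394 × 47 ≈ 1.9 patients.
- p = 0.02: 1 − 0.98^4 = 0.0776, and 0.0776 × 47 ≈ 3.6 patients.
- p = 0.05: 1 − 0.95^4 = 0.1855, and 0.1855 × 47 ≈ 8.7 patients.

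These count patients who miss a last-on-day dose. At each assumed p they are an upper bound on patients led to an off-day dose, since only someone who follows item 3 to the letter would take it.

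**Step 5: the design.** None of this enters the sample size calculation. The rule of 24 or more event-free patients out of 47, with null 0.38 and alternative 0.60, gives exact alpha 0.0466 and power 0.918. These match the stated 4.7% and 91.8%.

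**The case against.** The best defence is that item 3 should not be read alone. Item 1 of the same form sets the 5/2 schedule, so restarting can mean going back to that schedule, under which an off-day stays an off-day. Section 5.1 requires staff to tell the patient not to make a dose up the next day, and Section 8.1.5 requires them to make sure she understands. The diary comes back each cycle, so a dose entered on Day 6, 13, 20 or 27 would be seen. On this view the wording is at most ambiguous.

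Much of this stands. These safeguards make an off-day dose less likely, or visible afterwards. They do not change what item 3 says, and a patient who obeyed it on one of the four days would be departing from item 1 and from Section 5.1. Section 5.1 itself words the resumption rule differently for the two oral drugs. The diaries lose that distinction, which points to a sentence suited to a daily drug and not to a deliberate choice.

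Two further objections limit the size of the point. The patient counts in Step 4 rest on assumed miss rates. The fraction who would then take the off-day dose is unknown and could be zero. The CBC comparison in Step 3 is also weak evidence of harm: with the visit window, the C1D15 draw may fall anywhere from Day 12 to Day 18. A fully adherent patient could then have 0, 1 or 2 dose-free days before it.

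**Conclusion.** The inconsistency is real but minor. Read literally, item 3 contradicts Section 5.1 after a miss on 4 of the 20 dosing days per cycle and agrees with it on the rest. Each such miss can produce at most one off-day dose, within the planned total of 20. Any effect on the primary neutropenia rate is probably very small and cannot be estimated from the documents. The conclusion that the texts conflict depends only on the literal reading of item 3 and needs no assumed miss rate. It is worth correcting because it is a working dosing instruction for the schedule under study, but it casts no doubt on the trial's conclusions.

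**What to change.** Keep the first sentence of Appendix B item 3. Replace the second with: *Do not make it up; take your next dose on your next scheduled dosing day (Days 1-5, 8-12, 15-19, 22-26).* This agrees with Section 5.1 on all 20 dosing days, changes nothing for the 16 that already agree, and puts on the form the dosing days it now lacks. The letrozole diary can stay as it is. The cost is one sentence on a one-page form.

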APPENDIX C: LETROZOLE MEDICATION DIARY

Today's Date: _____

Agent: letrozole

Cycle: _____

Study ID#: _____

INSTRUCTIONS TO THE PATIENT:

1. Complete one form for each month. Take _____mg (___tablets) of letrozole daily with or without food, at approximately the same time each day. Take the letrozole with a glass of water and drink the glass of water in as little time as possible. Swallow the letrozole whole and do not chew them.
2. Record the date, the number of tablets taken, and when you took them.
3. If you forget to take your letrozole dose before 6:00PM, then do not take a dose that day. Restart taking it the next day.
4. If you have any questions or notice any side effects, please record them in the comments section. Record the time if you should vomit.
5. Please return the forms to your physician or your study coordinator when you go to your next appointment. Please bring your unused study medications and/or empty bottles with you to each clinic visit so that a pill count can be done.

Day	Date	What time was dose taken?	# of tablets taken	Comments
1				
2				
3				
4				
5				
6				
7				
8				
9				
10				
11				
12				
13				
14				
15				
16				
17				
18				
19				
20				
21				
22				
23				
24				
25				
26				
27				
28				

APPENDIX D: List of CYP3A4 Strong Inhibitors and Inducers
(<http://medicine.iupui.edu/clinpharm/ddis/clinical-table/>)

Inhibitors

Indinavir
Nelfinavir
Ritonavir
Clarithromycin
Itraconazole
Ketoconazole
Nefazodone
Lopinavir
Posaconazole
Saquinavir
Telaprevir
Telithromycin
Voriconazole
Grapefruit and grapefruit juice

Inducers

Carbamazepine
Efavirenz
Nevirapine
Phenobarbital
Phenytoin
Pioglitazone
Rifabutin
Rifampin
St. John's Wort
Troglitazone

APPENDIX E: OPERATING PROCEDURE FOR CTC COLLECTION

Standard Operating Procedure for Whole Blood Collection ----Kit Instruction for Use (for samples shipped to UCLA)

1 PURPOSE

1.1 Whole Blood Collection is intended for use to perform CTC testing from human blood samples.

2 SCOPE

2.1 Whole Blood Collection Kit is intended for professional use only, by a licensed phlebotomy technician.

3 DEFINITIONS AND ACRONYMS

3.1 N/A

4 RELATED PROCEDURES / FORMS

#	Procedure
SOP0013.2	Instructions for Shipping Human Blood Samples

5 SPECIMEN

5.1 N/A

6 REAGENTS

6.1 N/A

7 SUPPLIES

7.1 Supplies

Quantity	Description	Location	Storage upon arrival
1	One FedEx pouch contains one FedEx Express Package Airbill (pre-filled with addresses and priority Overnight checked) , see blood shipment SOP for detail	On top, between the Styrofoam and cardboard shipping boxes	Peel and stick the pouch on top of the cardboard box, retain the sender's copy, affix all the copies of the airbill in the pouch
3	The same FedEx pouch also contains three shipping labels: 1)Biomedical Material, 2)Exempt Human Specimen and 3) Keep refrigerated upon arrival , see blood shipment SOP for detail	On top, between the Styrofoam and cardboard shipping boxes	Peel and stick these three labels on the side of the cardboard box
2	In 1 small specimen bag (primary container), containing one Yellow top (ACD) blood tube, absorbent pad and	On top of ice gels, in Styrofoam box	RT or 4°C

	one 50 mL conical tube (secondary container). see Appendix Figure 1 and 2		
3	Three (3) big specimen bags with 3-4 ice gel packs in each specimen bag, see Appendix Figure 4	In Styrofoam box	4°C
2	The shipping boxes include one Styrofoam box (inside) and one cardboard box (outside), see blood shipment SOP for detail		RT or preferably at 4°C
1	Blood draw Instruction which is placed in the pouch of small specimen bag		RT

7.2 Equipment and Reagents to be Supplied by User

Quantity	Description
1	BD Vacutainer Safety-Lok Blood Collection Set with Pre-attached holder
1	Elastic band
2	Alcohol antiseptic
1	Gauze sponge
1	Band-aid
1	Instruction for Use

Do NOT use the kit if any damage of the package is observed.

8 QUALITY CONTROL

8.1 Whole Blood Collection Kit components should be obtained in one Biohazard-labeled plastic bag. Do NOT use the kit if any damage of the package is observed.

9 Blood Draw Instructions

Step	Action
	Upon kit arrival
1	Open the cardboard box and locate the FedEx pouch. See blood shipment SOP (instruction) for affixing the Airbill and shipping labels.
2	Open Styrofoam box, locate the small specimen bag which have blood collection tube and 50 mL conical tube. Place these items at room temperature, or keep them in the same Styrofoam box.
3	Store the gel ice packs in 4°C. Read blood draw instructions located in the pouch of the small specimen bag.
	Blood Draw Procedures
4	Collection and labeling: Draw 1 full tube of blood into the yellow top collection tube. Label the tube with 1) human blood; 2) date (11/17/16) and 3) study number (i.e: W001).
5	Place one blood tube into one 50 mL tube, making sure that the absorbent pad protects the blood tube between blood tube and 50 mL tube. Close the conical

	tube cap tightly. Place the 50 mL tube in the small specimen bag. Seal the specimen bag.
6	Take out all three big ice gel bags from 4°C. The first big ice gel bag is placed on the bottom of the Styrofoam shipping box. Place the two 50mL conical tubes in the second big ice gel bag which is put above the first ice gel bag. Seal the second bag completely. The third big ice gel bag will be placed on the top of the shipping box covering the two conical tubes. One can open the third big ice gel bag to evenly distribute the small ice gel in the shipping box.
7	Seal the shipping boxes tightly: Seal both inside (Styrofoam) and outside (cardboard) shipping boxes tightly with tape. See the SOP for blood shipment

10 Contact Information

Contact CytoLumina lab at **[contact]** or email [contact] with any questions.

11 Appendix

Figure 1. Picture of labeled tubes in sealed sterile.

Blood Draw Instruction (for customers)

A. Obtain blood draw items in the shipping box and in the hospital.

- a1. 1 - BD Vacutainer Safety-Lok Blood Collection Set with Pre-attached holder (not supplied by the kit)
- a2. 1 - Elastic band (not supplied by the kit)
- a3. 2 - Alcohol antiseptic (not supplied by the kit)
- a4. 1 - Band-aid (not supplied by the kit)
- a5. 1 - Gauze sponge (not supplied by the kit)
- a6. 1 - yellow top blood tube (supplied by the kit)
- a7. 1 – 50 mL conical tube with the absorbent pads as the secondary containers for protecting blood tube (supplied by the kit)
- a8. 1- small specimen bag. Each 50 mL conical tube is always placed in each small specimen bag
- a9. Ice gel packs in three big specimen bags must be stored in refrigerated (4°C) at least 12 hours before blood draw.

B. Blood Draw Procedure:

- b1. Collection and label: Draw 1 full tube of blood into the yellow top collection tube. Label the tube with 1) human blood; 2) date (11/17/16) and 3) study number (i.e: W001)
- b2: Place one blood tube into one 50 mL tube, making sure that the absorbent pad protects the blood tube in between blood tube and 50 mL tube. Close the conical tube cap tightly. Place the 50 mL tube in the small specimen bag. Seal the small specimen bag.
- b3. Take out all three big ice gel bags from 4°C. The first big ice gel bag is placed on the bottom of the Styrofoam shipping box. Put the ice gel bag with blood tubes in the middle. Seal the middle big specimen bag tightly. The third big ice gel bag will be placed on the top of the shipping box covering the blood tube/50 mL conical tube.
- b4: Seal the shipping boxes tightly: Seal both inside (Styrofoam) and outside (cardboard) shipping boxes tightly with tape. See the SOP for blood shipment

